#### 3.4.2 Description of Procedures

- Medical history: a review of treatment history, any ongoing medical conditions, and medical history pertaining to eligibility on study and involvement during the study.
- Physical exam: review of organ systems, weight, and vital signs (i.e., temperature, pulse, respirations, blood pressure, and oxygen saturation). After initiation of study drug, symptom-directed physical examinations will be performed as clinically indicated in the investigator's judgment. Note: Height will only be required prior to treatment no later than Cycle 1 Day 1.
- Performance status (ECOG and Karnofsky): an assessment of activities of daily living; see [Appendix A](#).
- Laboratory assessments: the following comprises the required tests/analytes. These assessments may be performed at Clinical Laboratory Improvement Amendments (CLIA) (or equivalent) certified laboratories outside the enrolling site and results forwarded to the study team for review and management. Given that the methodologies utilized are similar

across all laboratories, no significant variability is expected and there is no anticipation that study data will be affected.

However, as different laboratories use slightly different kinds of equipment, each laboratory must determine/validate its own reference ranges. Therefore, on this protocol, normal ranges from each lab will be used in reference to terms such as ULN, except in cases where absolute values are appropriate and are specified as such. Note: Panels containing the tests below may be ordered in lieu of individual tests.

- CBC with differential: includes Neutrophils, Lymphocytes, Monocytes, Eosinophils, Basophils, WBC, RBC, Hemoglobin, Hematocrit, RBC Indices, MCV, RDW, Platelet.
- Blood chemistries: includes Sodium (Na), Potassium (K), Chloride (Cl), Total CO2 (bicarbonate), Creatinine, Glucose, Urea nitrogen (BUN), Albumin, Calcium total, Magnesium total (Mg), Inorganic Phosphorus, Alkaline Phosphatase, ALT/GPT, AST/GOT, Total Bilirubin, Direct Bilirubin, Total Protein will be performed to assess organ function for safety
- HIV, HBV, HCV – infectious disease serologies as per section [2.2.2](#)
- Vitamin B12, Folate, copper, zinc, TSH, free T4- to assess alternative/reversible causes of cytopenias that may confound MDS diagnosis at screening
- Reticulocyte count
- Urinalysis: for safety

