- **Overall Side Effect Bother** (see Study Instrument packet/[Appendix H](#)): FACIT Measurement System Item GP5 'I am bothered by the side effects of treatment', is a single item summary index of bother that has demonstrated association with clinician-reported adverse events and with participants' ability to enjoy their lives that can help to adjudicate the variability in adverse effects across treatments being compared with each other [7]. Completion of this item will take less than a minute. This will be completed weekly for the first two cycles, at response evaluation, at disease progression, at the end of treatment and post therapy follow-up.
- **Patient Global Impression of Severity (PGI-S)** (see Study Instrument packet/[Appendix H](#)): The Patient Global Impression of Severity (PGI-S) is a global index that may be used to rate the severity of a specific condition (a single-state scale). It is a simple, direct, easy to use scale that is intuitively understandable to clinicians. It has been validated in studies of incontinence [8]

and insomnia[9]. For this study, we will ask participants to rate the severity of their symptoms using a 5-point scale (0-none, 1-mild, 2-moderate, 3-severe, 4-very severe) that will take less than a minute on average to complete. This will be completed at baseline, weekly for the first two cycles, at response evaluation, at disease progression, at the end of treatment and post therapy follow-up.

- **Patient Global Impression of Change (PGI-C)** (see Study Instrument packet/[Appendix H](#)): Patient Global Impression of Change (PGI-C) aims to quantify disease activity relative to an anchor point. Specifically, participants are asked to calculate the difference between their current and previous health state based on a Likert scale. Although PGI-C scales typically comprise between 7 and 11 points which show optimal participant preference, discriminative ability and test-retest ability, they can be tailored to specific conditions and disease parameters as per the clinicians' needs [10]. For this study, we will ask participants to rate their global impression of change in their symptoms since their last visit using a 5-point scale (1-much improved, 2-improved, 3-no change, 4-worse, 5-much worse). Completion of this item will take less than a minute on average. This will be completed weekly for the first two cycles, at response evaluation, at disease progression, at the end of treatment and post therapy follow-up.

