3.5.2 Phase I and II – Cycle 2 – beyond

Procedure	Cycles 2-3					Cycles $\geq 4$			At Disease Progression	End of Treatment	Post-therapy follow-up 	End of Study
	Day 1	Day 8	Day 15	Day 22	Day 28	Day 1	Day 8	Day 28				
Window(s):	-3 days	$\pm 3$ days	$\pm 3$ days	$\pm 3$ days	$\pm 3$ days	-3 days	$\pm 3$ days	$\pm 3$ days	$\pm 3$ days	$30+7$ days	See note.	
Physical exam	X		X			X				X		
Vital signs 	X		X			X				X		
Height												
Weight	X		X			X				X		
Performance score												
Chemistries 	X		X			X			X	X		
CBC/differential	X		X			X			X	X		
Reticulocyte count	X					X			X	X		
Pregnancy test	X					X						
Urinalysis	X					X				X		
Bone marrow biopsy and aspirate 					X 			X 	X			
TBNK panel 	X					X			X	X		
Peripheral blood flow cytometry									X 			
Next gen seq- myeloid panel					X 			X 	X			
Correlative research studies (see Section 5.1)	X		X 		X 	X		X 	X	X		
Inqovi administration 	X					X						
KPT-8602 administration 		X	X				X					
Response evaluation 	X					X						
Transfusion dependency assessment	X		X			X			X	X		
Adverse event assessment	X	X	X	X	X	X		X	X	X		
Concomitant-medications	X		X			X				X		
PRO: NIH MDS Adult Psychosocial assessment 					X			X		X		
PRO: EORTC-QLQC30 	X				X	X		X	X	X	X	
PRO: PRO-CTCAE 	X	X	X	X	X	X		X	X	X	X	
PRO: Overall Side Effect Bother 					X	X		X	X	X	X	
PRO: PROMIS Physical Function 	X	X	X	X	X	X		X	X	X	X	
PRO: PGI-S 	X	X	X	X	X	X		X	X	X	X	

Procedure	Cycles 2-3					Cycles ≥4			At Disease Progression	End of Treatment	Post-therapy follow-up 	End of Study
	Day 1	Day 8	Day 15	Day 22	Day 28	Day 1	Day 8	Day 28				
Window(s):	-3 days	±3 days	±3 days	±3 days	±3 days	-3 days	±3 days	±3 days	±3 days	30+7 days	See note.	
PRO: PGI-C 					X	X		X	X	X	X	
Survival											X	X

Follow-up will occur via phone call every 3 months (+/- 2 weeks) for the first 24 months, then every 6 months (+/- 4 weeks) for 3 years, then annually for up to 8 years. Overall survival, event-free survival, progression-free survival, and treatment status will be assessed at all timepoints.

Includes temperature, blood pressure, heart rate, respiratory rate, oxygen saturation

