Longitudinally describing and evaluating disease and treatment-related symptom severity and functional well-being: We will use two graphical approaches to address this objective. First, Locally weighted regression (LOWESS) curves showing symptom trajectories over time for each symptom scales and functional well-being subscales from the EORTC-QLQ C30 will be constructed. Second, we will also construct individual participant profiles for each of the EORTC QLQ C30 symptom scales and functional well-being subscales to describe the individual participants' patterns of change over time. Effect sizes that standardize the difference in symptom improvement or worsening between two preselected time points will be calculated.

Determining meaningful change in disease and treatment related symptoms and functional well-being by using anchors: In order to determine meaningful change in the EORTC QLQ C30 symptom scales and functional well-being subscales, we will use both clinician-rated (Karnofsky) and patient-rated (PGI-Severity, PGI-Change) anchors. We will stratify patients into 3 change groups (improved, no change, declining) between pre-selected time points (e.g. baseline and end of first disease evaluation). The difference in the EORTC QLQ C30 symptom scale scores and functional well-being subscale scores between the pre-selected time points within each of the change groups provide an estimate of meaningful change.

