## 17.9 APPENDIX I: DATA ELEMENTS TO CONSIDER FOR CRF ENTRY IN CLINICAL DATABASE

### Participant characteristics at protocol entry

- Sex (male, female)
- Age at enrollment (number)
- Ethnicity (white, black, American Indian/Alaskan native, Asian/Pacific islander, Hispanic, other)
- ECOG and Karnofsky performance status
- Diagnosis - MDS (high risk and higher intermediate risk)
- 2016 WHO classification of MDS (MDS with single lineage dysplasia [MDS-SLD], MDS with ring sideroblasts and single lineage dysplasia [MDS-RS-SLD], MDS with ring sideroblasts and multilineage dysplasia [MDS-RS-MLD], MDS with multilineage dysplasia [MDS-MLD], MDS with excess blasts [MDS-EB], MDS with isolated del(5q), MDS unclassifiable [MDS-U],
- Date of MDS diagnosis (month, year)
- Age at MDS diagnosis
- Revised International Prognostic Scoring System (IPSS-R) score at MDS diagnosis
- Cytogenetic profile at diagnosis and enrollment, if available (see Appendix C)- only need overall score (very good, good, intermediate, poor, very poor)
- Bone marrow blasts %, if available (flow/asp and IHC/bx)
- Hemoglobin, if available (at diagnosis and at enrolment) use counts from day of bone marrow for enrollment
- Platelet count, if available (at diagnosis and at enrolment) day of bone marrow for enrollment
- Absolute neutrophil count (ANC), if available (at diagnosis and at enrolment) day of bone marrow for enrollment
- RBC transfusion dependence (transfusion dependent or independent)
- Platelet transfusion dependence (transfusion dependent or independent)
- Average # of transfusions per month (RBCs units and instances of platelets transfusions) in the 3 months leading up to baseline on study
- Laboratory values will be collected from time of screening for duration of trial
- TP53 mutation status at enrollment, if available (TP53 mutation positive or negative)
- Names and # of cycles of prior Lines of therapy for MDS.
- Response to most recent line of therapy: CR (complete response), PR (partial response), HI (hematologic improvement), mCR with HI (marrow CR with hematologic improvement), mCR without HI (marrow CR without hematologic improvement), SD (stable disease), PD (disease progression)
- MDS-CI (low risk, intermediate risk, high risk)
- Rockwood frailty index (see Clinical Frailty Scale)

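### Karnofsky is named as an anchor for meaningful change but is not scheduled after Cycle 1 Day 1, and PGI-C does not span the plan's example interval, so only PGI-S covers it

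*Combined protocol and SAP*

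**What the plan says.** Section 10.4.9.1 sets out the anchor analysis for the QLQ-C30 symptom and functional scales. It names one clinician-rated and two patient-rated anchors: "we will use both clinician-rated (Karnofsky) and patient-rated (PGI-Severity, PGI-Change) anchors". The anchors define groups: "We will stratify patients into 3 change groups (improved, no change, declining"), formed "between pre-selected time points (e.g. baseline and end of first disease evaluation"). The change in QLQ-C30 score within each group is then the estimate of meaningful change.

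The anchors are described and scheduled elsewhere:

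- **Karnofsky.** Section 3.4.2 lists "Performance status (ECOG and Karnofsky): an assessment of activities of daily living" and gives no on-treatment timing. The calendar in section 3.5.1 marks it at screening, baseline and C1D1. In section 3.5.2 the row "Performance score" carries no mark. Appendix I lists "ECOG and Karnofsky performance status" among the entry characteristics only.
- **PGI-C.** Section 3.4.3 asks participants to "rate their global impression of change in their symptoms since their last visit".
- **PGI-S.** Section 3.4.3 describes a five-point rating of symptom severity, collected at baseline, weekly in the early cycles and at response evaluation.

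**The concern.** An anchor can classify change over an interval in two ways. A state rating, such as Karnofsky or PGI-S, needs a value at both ends. A change rating, such as PGI-C, needs a recall period that matches the interval.

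Karnofsky fails the first condition for any interval that ends on treatment. PGI-C fails the second for the only interval the plan names. A participant who improved in the first weeks and then held steady would correctly answer that nothing had changed since the last visit, and would be put in the unchanged group while the QLQ-C30 score showed improvement from baseline. That would distort the estimate of meaningful change.

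Determining meaningful change by anchors is a stated exploratory objective (sections 1.1.3 and 10.1). Karnofsky is its only clinician-rated anchor. Ratings not made at the visit cannot be recovered systematically afterwards.

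**Working it through.** The plan gives no figure to reproduce. The check sets each anchor's schedule against the interval in section 10.4.9.1.

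**Assumptions.** Nominal visit days, without visit windows. Baseline is 0 to 7 days before C1D1 (section 3.4.1). The first disease evaluation is taken as C1D28 in Phase I and C2D28 in Phase II, the first marrow time points in the calendar footnotes.

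**Length of the interval**

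- Baseline to C1D28: 28 − 1 = 27 days, plus 0 to 7, giving 27 to 34 days.
- Baseline to C2D28: 27 + 28 = 55 days, plus 0 to 7, giving 55 to 62 days.

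**Karnofsky.** The scheduled values are screening, baseline and C1D1. The number scheduled after C1D1 is 0, including at disease progression and end of treatment. No change score can be formed to either evaluation.

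**PGI-C.** Share covered = look-back days ÷ interval days.

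- At C1D28, last visit D22: look-back 28 − 22 = 6 days. 6/34 = 18% and 6/27 = 22%.
- At C2D28, last visit C2D22 or C2D15 (the documents do not say which contact counts): look-back 6 or 13 days. The extremes are 6/62 = 10% and 13/55 = 24%.
- The PGI-C schedule is itself stated in three ways: weekly for two cycles (section 3.4.3), weekly for three cycles (footnote 20 to section 3.5.2), and Day 28 only in cycles 2 and 3 (the calendar row). If the last visit is read as the previous PGI-C completion under the Day-28-only row, the look-back at C2D28 is 28 days, and 28/62 = 45% to 28/55 = 51%. On no reading is the interval spanned.

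**PGI-S.** Scheduled at baseline, and at both C1D28 and C2D28 under section 3.4.3 and footnote 19. A change score can be formed over the whole interval.

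| Anchor | Start of interval | First disease evaluation | Covers the example interval |
|---|---|---|---|
| Karnofsky | yes | not scheduled | no |
| PGI-C | not applicable (change item) | yes, recall to last visit | no |
| PGI-S | yes | yes | yes |

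One of three anchors covers the example interval.

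**The case against.** **The blank calendar row may be lost in text extraction.** This is possible but unlikely. Appendix I puts performance status at entry and omits it from the on-treatment and follow-up lists, and section 3.4.2 gives no later timing. The height row in the same table is also blank, and there section 3.4.2 confirms that height is required only before treatment.

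**A reader might infer that no planned anchor covers the interval, or that the objective cannot be met.** The documents do not support that. PGI-S is scheduled at both ends, and the analysis can be run on it.

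**A reader might also infer that PGI-C is unusable.** That goes too far as well. Section 10.4.9.1 leaves the time points to be chosen and gives baseline to first disease evaluation only as an example. PGI-C fits an interval between consecutive visits, provided QLQ-C30 is scored at both ends. The item itself is in the Study Instrument Packet, which is not part of these documents, so the recall period rests on the description in section 3.4.3. What stands is a mismatch with the one interval the plan names.

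**Materiality is low.** This is one of many exploratory objectives, and section 10.4.9 analyses them descriptively. That is accepted and sets the weight of the point.

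**Conclusion.** The point holds in this form. Karnofsky cannot serve as an anchor under the current schedule, because it has no scheduled assessment after C1D1. PGI-C does not span the example interval: on nominal days it covers about 18 to 22% of it at C1D28 and about 10 to 24% at C2D28, or at most about half on the most generous reading of the schedule. For that interval the analysis rests on PGI-S alone, a single five-point patient rating with no clinician rating to set beside it. It would be split into three groups among at most 18 + 43 = 61 planned evaluable participants.

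The Karnofsky finding does not depend on which on-treatment time points are chosen. The PGI-C finding depends on the example interval being used and on the recall wording in section 3.4.3. The point is minor: it touches an exploratory analysis and leaves the primary endpoint, sample size and safety as they are.

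**What to change.** 1. In the section 3.5 calendar, mark performance score (ECOG and Karnofsky) at the first disease evaluation (C1D28 in Phase I, C2D28 in Phase II) and at the later QLQ-C30 visits: C3D28, C6D28, C9D28, C12D28, C24D28 and end of treatment. Starting only at C3D28 would miss the interval in question.
2. Add performance status to the on-treatment data list in Appendix I.
3. In section 10.4.9.1, use change in PGI-S and Karnofsky for intervals from baseline to an evaluation, and use PGI-C only for intervals between consecutive PGI-C visits. The PGI-C stem need not be reworded.
4. While the calendar is open, reconcile the three PGI-C schedules. Also confirm QLQ-C30 at C2D28: the calendar row marks it and section 3.4.3 places it at response evaluation, but footnote 18 lists no visit before C3D28.

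The cost is a brief clinician rating at visits already planned, one more data item, and a protocol amendment with IRB approval. If the sponsor does not want the extra rating, the alternative is to drop Karnofsky as an anchor in section 10.4.9.1 and state that baseline-to-evaluation change rests on PGI-S. That costs only text but leaves the objective without a clinician-rated anchor.

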## **11 COLLABORATIVE AGREEMENTS**

### **11.1 AGREEMENT TYPE**

This study will be conducted under an Umbrella Collaborative Research and Development Agreement (CRADA) with Karyopharm Therapeutics, Inc (#03377).

## **12 HUMAN SUBJECTS PROTECTIONS**

### **12.1 RATIONALE FOR PARTICIPANT SELECTION**

No participants will be excluded from participation based on gender, race or ethnicity. The study will be open to all participants who satisfy the inclusion criteria and provide an informed consent to the protocol.

Participants with active HIV, HCV, or HBV are excluded because study treatment can pose more risks for these participants.

Due to the unknown effects of KPT-8602 on the fetus and infants, and known teratogenicity of Inqovi, women of reproductive age will only be allowed to enroll if they commit to following a strict manner of contraception; Females who are breast-feeding will not be eligible for the trial. Men who are sexually active with women of childbearing age will also have to commit to strict contraceptive practices while on study.

## **12.2 PARTICIPATION OF CHILDREN**

Children will not be eligible for participation in this study due to lack of adequate safety data in children. Biologic rationale and preclinical work were validated in adult population and would need reanalysis in children, where MDS may arise more so from inherited bone marrow failure syndromes than in adults and have a different pathophysiology.

## **12.3 RISK/BENEFIT ASSESSMENT**

### **12.3.1 Known Potential Risks**

All known potential risks associated with KPT-8602 from prior experience in humans has been discussed in Section **14**. In the first-in-human study of KPT-8602 monotherapy, the most frequently occurring AEs were gastrointestinal effects (nausea, fatigue, diarrhea, decreased appetite, weight decreased) and cytopenias (thrombocytopenia, anemia). The potential risks of Inqovi are noted in the USPI for INQOVI and includes myelosuppression and embryo-fetal toxicity. However, there is an unknown element here which is why this is a phase I safety study and participants will be closely monitored for all AEs.

Other risks involved in the study include that of standard MDS procedures, including regular blood draws and bone marrow evaluations. These are invasive procedures that carry with them the risk of infection, bleeding and damage to surrounding tissues/organs. Phlebotomy and bone marrow evaluations will be conducted by well-trained personnel who follow sterile techniques to minimize complications.

#### **12.3.1.1 Risks related to study procedures**

##### **12.3.1.1.1 Blood samples**

Minor complications including bleeding, pain, and hematoma formation at the site of blood draws, or infections may rarely occur. Up to 82 mL of blood may be collected at one time, no more than 250 mL will be collected over an 8-week period.

##### **12.3.1.1.2 Bone marrow aspiration/biopsy**

The bone marrow aspiration and biopsy may cause pain, bruising, bleeding and infection. Soreness near the site may last for a couple of days after the procedure. The subject may have more pain, risk of bleeding and bruising if he/she complete both aspiration and biopsy rather than just the aspiration. The subject should contact the study team immediately if pain is severe or fever develops.

##### **12.3.1.1.3 Electrocardiogram**

Other than possibly experiencing some minor skin irritation from the electrodes there are no anticipated risks related to complete the electrocardiogram and/or the echocardiogram.

##### **12.3.1.1.4 Intravenous catheter**

The risks of IV insertion include temporary pain and bleeding or bruising at the site where the IV enters the skin. In placing the IV, there is a small chance of fluid leaking into the tissue surrounding the IV and infection, which may cause some swelling and discomfort. Rarely, the IV site may become infected, which might require treatment with antibiotics.

#### 12.3.1.1.5 Questionnaires

Some of the questions in the questionnaire may be upsetting or make subjects feel uncomfortable. Subjects can skip any of the questions he/she does not want to answer, and can stop at any time.

#### 12.3.1.1.6 Urine collection

No physical risks are associated with urine collection.

#### 12.3.1.1.7 Losing data

This includes the risk that data obtained during this study can be released to members of the public, insurers, employers, or law enforcement agencies. Although there are no plans to release results to the participants, family members, or health care providers, this risk will be included in the informed consent document.

### 12.3.2 Known Potential Benefits

Due to the significant preclinical and prior clinical experience with KPT-8602, this study hypothesis has strong evidence that KPT-8602 may have disease-modifying beneficial therapeutic activity in MDS. If this is confirmed via this trial, participants have the potential for immediate-benefits that include, improved cytopenias, less transfusion- and growth factor-dependence, less complications of cytopenias such as infections and hemorrhagic complications. Transfusion independence also leads to improved quality of life. Long-range potential benefits, should our investigational agent confirm efficacy, include stability of MDS disease with improved quality of life and potential for less progression into AML, which is associated with significant morbidity and mortality.

